9.6.1.7.2 Treatment of arterial hypertension associated with copanlisib

Subjects with pre-existing arterial hypertension should adhere to their regular antihypertensive medication schedule, and take their usual doses on the day of the copanlisib infusion. The management of acute arterial hypertension following copanlisib will need to be individualized for each subject, but the experience in Phase I studies on copanlisib has suggested the benefit of dihydropyridine calcium channel blockers (i.e. amlodipine, felodipine). Topical nitrates, verapamil and diltiazem (nondihydropyridine calcium channel blockers) can be also considered.

In general, antihypertensive medication should be readily available if needed. If arterial hypertension $\geq 150/90$ mmHg occurs during the copanlisib infusion, antihypertensive treatment is suggested as indicated above. If arterial hypertension ($\geq 160/100$ mmHg) occurs during copanlisib IV infusion, the copanlisib IV infusion should be interrupted or slowed down, administration of anti-hypertensive therapy initiated and copanlisib infusion may be resumed when BP has returned to $<150/90$ mmHg.

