13. Administration of strong CYP3A4 inhibitors or inducers within 2 weeks prior to dosing until 7 days after dosing (A list of these medications can be found in Section 16.8 of the protocol. However, this list may not be comprehensive); the label of the respective co-medications should therefore be checked).
14. Use of immunosuppressive drugs.
15. Administration of medications that prolong the QT interval within 2 weeks prior to dosing and during the study (A list of agents that prolong the QT interval can be found at <https://crediblemeds.org/healthcare-providers/>. However, this list may not be comprehensive); the label of the respective co-medications should therefore be checked).
16. Intake of foods or beverages containing grapefruit, pomelo or Seville oranges within 7 days before study drug administration and 7 days thereafter. The juices and products containing these fruits must also be avoided.
17. Regular daily consumption of more than 1 L of methylxanthine-containing beverages.
18. Unable to abstain from alcohol and methylxanthine-containing beverages or food (coffee, tea, cola, chocolate, "powerdrinks") from 48 h prior to dosing of study drug until Day 7.
19. Subjects with known drug abuse within 1 month prior to dosing or evidence of such abuse as indicated by the laboratory assays conducted during the screening or baseline evaluations.
20. Donation or loss of 400 mL or more of blood within 4 weeks prior to dosing.

Electrocardiogram (ECG)

21. Abnormal finding in the 12-lead electrocardiogram (ECG), such as QTcF (Fridericia correction) interval over 500 msec, or any other finding that increases the risk associated with study participation, as judged by the investigator.

Laboratory examination

22. Neutrophils <1500/ μ L¹⁶ at inclusion.
23. Positive urine drug screening at screening and Day -1.

Other exclusion criteria

24. Previous assignment to treatment during this study.
25. Close affiliation with the investigational site; e.g. a close relative of the investigator, dependent person (e.g. employee or student of the investigational site).
26. Criteria which in the opinion of the investigator preclude participation for scientific reasons, for reasons of compliance, or for reasons of the subject's safety.
27. Inability to understand the protocol requirements, instructions and study related restrictions, the nature, scope, and possible consequences of the study.
28. Subject is in custody by order of an authority or a court of law.

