7.4.2 Selection and timing of dose for each subject

Each of the subjects will receive one single dose of 12 mg of copanlisib i.v. over 1 h.

In case of a blood pressure value of \geq 150/90 mmHg before the planned time point of dosing administration will be delayed until recovery to $<$ 150/90 mmHg. Instructions for blood pressure measurements are given in Section 9.6.3.

Antihypertensive medication may be given to control arterial hypertension. Dosing can proceed on the scheduled day if at least 2 consecutive blood pressure values measured at 5 to 10 min interval prior to copanlisib dosing show BP $<$ 150/90 mmHg. Otherwise, dosing must be delayed. Guidance for the treatment of arterial hypertension is given in Section 9.6.1.7.2.

Subject's fasting pre-dose glucose level should be \leq 125 mg/dL (non-diabetic subjects) or $<$ 160 mg/dL (diabetic subjects) before copanlisib infusion (see Section 3, benefit-risk assessment). Guidance for the treatment of transient glucose increase is given in Section 9.6.1.7.1.

Food and drink on the day with dosing will be standardized. For details on meals, see Section 9.2.6.2.

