8.1 Prior and concomitant therapy

All prior medication used within 6 weeks before treatment will be documented (medication history). Copanlisib is metabolized by CYP3A4. Therefore, concomitant use of strong inhibitors of CYP3A4 or strong inducers of CYP3A4 is not permitted from 14 days before the administration of study drug until 7 days after dosing (end of blood sampling period for PK). Refer to Section 6.2 for medication representing exclusion criteria. A list of these medications can be found in Section 16.8 of the protocol.

Use of medication for concomitant therapy is not planned. Especially the use of medication that may have an impact on the study objectives is not permitted. This comprises any medication (including herbal remedies or food supplements), which could affect the pharmacokinetics and / or pharmacodynamics of the study drug. The subjects will be instructed to report any concomitant medication used to the investigator. All concomitant medication will be documented.

The subjects with hepatic and renal impairment will be allowed to continue their medications as long as they are in line with the enrollment criteria.

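### The blood pressure guidance suggests verapamil and diltiazem, which the protocol lists as moderate CYP3A4 inhibitors; this conflicts with the general clause of 8.1 and could slightly raise AUC in impaired subjects.

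*Protocol*

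**What the plan says.** **Before dosing.** Protocol 7.4.2 delays dosing while blood pressure is 150/90 mmHg or higher. It adds: "Antihypertensive medication may be given to control arterial hypertension". It then refers the site onward: "Guidance for the treatment of arterial hypertension is given in Section 9.6.1.7.2".

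**The guidance.** Protocol 9.6.1.7.2 first names two dihydropyridines, amlodipine and felodipine, on the strength of Phase I experience. It continues: "Topical nitrates, verapamil and diltiazem (nondihydropyridine calcium channel blockers) can be also considered". The same list applies if pressure reaches 150/90 mmHg during the infusion.

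**The inhibitor table.** Table 16-5 rates verapamil and diltiazem Moderate and amlodipine Weak. Felodipine and nitrates are not listed.

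**The rules on co-medication.** Section 8.1 holds two rules:
- A CYP3A4-specific rule bars strong agents only. Exclusion criterion 13 matches it: "Administration of strong CYP3A4 inhibitors or inducers within 2 weeks prior to dosing until 7 days after dosing". So does the heading of 16.8.
- A general clause disallows medication that may affect the study objectives: "This comprises any medication (including herbal remedies or food supplements), which could affect the pharmacokinetics and / or pharmacodynamics of the study drug".

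Impaired subjects "will be allowed to continue their medications as long as they are in line with the enrollment criteria". Criterion 16 separately excludes "Intake of foods or beverages containing grapefruit, pomelo or Seville oranges within 7 days before study drug administration and 7 days thereafter".

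**The analysis.** SAP 6.3.1 fits an ANOVA with group as the only factor. SAP 6.1.4 tabulates co-medication by frequency and does not link it to individual exposure.

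**The concern.** CYP3A4 carries more than 90% of copanlisib metabolism (Protocol 3), and the study exists to measure how organ impairment changes exposure. A CYP3A4 inhibitor started around dosing pushes AUC in the same direction as impaired elimination. A one-factor model cannot separate the two.

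The routing makes this possible. A site treating high blood pressure is sent from 7.4.2 to 9.6.1.7.2, which offers two moderate inhibitors. Section 9.6.1.7.3, on vomiting and diarrhea, points to 8.1 for permitted therapy; the hypertension section has no such pointer.

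Use may also be uneven between groups. Criterion 33 keeps nearly all medication from healthy controls for at least 2 weeks before dosing, so new pre-dose treatment would be expected mainly in impaired subjects. That is an inference, since 7.4.2 itself names no group. Post-dose treatment could occur in any group.

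At stake are the AUC and AUC(0-168) ratios, which are meant to inform labelling. Little effect on Cmax is expected, because itraconazole, a strong inhibitor, left it unchanged.

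**Working it through.** **Inputs from the documents**
- SD of log AUC(0-168): 0.40. Impaired group sizes: 8, 8 and 6 (Protocol 10.4, SAP 7).
- Itraconazole at the 12 mg dose: AUC up 1.41-fold (Protocol 3).
- Two-level group factor and 90% CI from PROC GLM (SAP 6.3.1).

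**Assumed, because the documents give neither**
- Effect R of a moderate inhibitor on AUC: 1.1 to 1.41. The top value belongs to a barred strong inhibitor, so it serves as a ceiling.
- Users k: 1 or 2 in one impaired group, none among controls, with full inhibition over the whole curve.

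**Step 1: reproduce the plan's intervals.** Limits are ratio × exp(± t × SE), with SE = 0.40 × √(2/n).
- n = 8: SE = 0.200. With 7 df, t = 1.895, and ratio 1 gives 0.685 to 1.461, as in Table 10-1.
- n = 6: SE = 0.231. With 5 df, t = 2.015, and ratio 1 gives 0.628 to 1.593, as in Table 10-2.

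The tables therefore use n − 1 df. The SAP's two-group model has 2n − 2: 14 df for 8 versus 8 (t = 1.761) and 10 df for 6 versus 6 (t = 1.812).

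**Step 2: shift of the ratio, R^(k/n)**

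| R | 1 of 8 | 2 of 8 | 1 of 6 | 2 of 6 |
|---|---|---|---|---|
| 1.1 | 1.012 | 1.024 | 1.016 | 1.032 |
| 1.2 | 1.023 | 1.047 | 1.031 | 1.063 |
| 1.41 | 1.044 | 1.090 | 1.059 | 1.121 |

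In standard errors, (k/n) × ln R / SE, the shift runs from 0.012/0.200 = 0.06 to 0.086/0.200 = 0.43 for n = 8. For n = 6 it runs from 0.016/0.231 = 0.07 to 0.115/0.231 = 0.50.

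**Step 3: effect on the upper limit, two users at 1.2-fold, SAP model df**
- 8 versus 8, ratio 1.3: 1.3 × exp(1.761 × 0.200) = 1.849; × 1.0466 = 1.935.
- 6 versus 6, ratio 1.2: 1.2 × exp(1.812 × 0.2309) = 1.824; × 1.0627 = 1.938.

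Neither passes 2. At ratio 1.3 with 6 versus 6, the limit without any inhibitor is already 1.976. There a rise of 2/1.976 − 1 = 1.2% would pass 2 (1.976 × 1.0627 = 2.100), but that row has almost no room to begin with, and the plan's own figure for it is 2.07.

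**Step 4: effect on the plan's stated chance.** By simulation with 8 versus 8, a true ratio of 1 and 14 df, the chance that the 90% CI lies within 50-200% is 0.90, which matches the plan. With 2 of 8 users at the 1.41 ceiling it is 0.87.

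**Step 5: would a re-analysis without users detect it?** Dropping k of n subjects changes the group's log mean by chance with SD 0.40 × √(1/(n−k) − 1/n). That is 0.053 (k = 1) or 0.082 (k = 2) for n = 8, and 0.073 or 0.115 for n = 6. The expected change, (k/n) × ln R, is 0.012-0.086 or 0.016-0.115. Noise is about as large as the signal at the ceiling and larger below it, so such a re-analysis would not be informative.

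**The case against.** **Moderate inhibitors are permitted.** Every CYP3A4-specific statement (8.1, criterion 13, 16.8) bars strong agents only, and 9.6.1.7.2 agrees with that choice. A reader might infer that the protocol breaches its own CYP3A4 ban; the documents do not support that. What remains is a conflict with the general clause of 8.1.

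**The preferred drugs already come first.** The dihydropyridines are named ahead of verapamil and diltiazem, and amlodipine is itself a weak inhibitor. This stands: the gain is modest, and the alternatives reduce the problem rather than remove it. Criterion 13 also says the inhibitor list may be incomplete, so a drug's absence from it is not proof of no effect.

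**New treatment is unlikely.** Criterion 8 excludes uncontrolled hypertension. Criteria 43 and 70 exclude hepatic subjects whose chronic medication changed within 4 weeks. Criterion 21 asks for a 14-day stable regimen for renal impairment. The protocol expects a very low probability of the class events, hypertension among them, after 12 mg. This largely stands, although that expectation concerns events after dosing, not pressure already raised beforehand.

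**The size is assumed and leans high.** Users are placed in one impaired group only, and full inhibition is applied to the whole curve. Treatment started after dosing would act on part of it. This stands.

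**A crossing of 2-fold.** A reader might multiply the plan's tabulated limit for N=6 at ratio 1.2 (1.911) by 1.063, obtain 2.031, and infer that two users at 1.2-fold would break the benchmark. That result depends on the 5 df behind Table 10-2. The SAP model has 10 df and gives 1.938. The benchmark is also not a decision rule, since the SAP plans no confirmatory analysis.

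**Users can be traced.** All co-medication is recorded and all data are listed, so individual users could be found by hand. That is true, but it does not remove the bias from the ratio.

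**Conclusion.** The point holds as a low-severity improvement. Section 9.6.1.7.2, reached from 7.4.2, suggests two drugs that the protocol's own table rates as moderate CYP3A4 inhibitors. The general clause of 8.1 argues against them; the CYP3A4-specific rules do not.

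New use around dosing in impaired subjects could raise AUC and AUC(0-168) by about 1-9% (8 subjects) or 2-12% (6 subjects), at most half a standard error. These figures rest on the assumed number of users, effect size, one-sided use and whole-curve inhibition, and their upper ends overstate. The documents do not show that such use will occur or that it would change a conclusion. It is worth preventing because the bias has a known direction, the planned model cannot separate it, and prevention is cheap.

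**What to change.** 1. **Protocol 7.4.2 and 9.6.1.7.2.** For blood pressure treatment newly started between screening and the 168 h PK sample, use felodipine, a topical nitrate or amlodipine (rated Weak) first. Use verapamil or diltiazem only if these fail or cannot be given. Subjects already taking either may continue.
2. **Protocol 8.1.** Replace the two conflicting rules on CYP3A4 with one: strong agents barred; new moderate agents avoided until the 168 h sample unless medically needed; stable moderate agents of impaired subjects allowed.
3. **Optional, SAP 6.1.4 and 6.3.1.** Mark users of moderate CYP3A4 agents in the listings and in the planned plots of exposure against organ function. This gives context and changes no estimate. A repeat ANOVA without users is not recommended (Step 5).

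**Cost:** a few sentences. No subject is lost, no interval widens, matching is untouched and no new data are needed. The downside is that two rescue drugs become second line until about a week after dosing, though they stay available when needed. Chronic verapamil or diltiazem in impaired subjects would remain possible, so the fix removes only the avoidable part of the bias.

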9.2.4 Treatment period

In case more than one measure/ action to be performed coincide at a given time point, the following order will be adhered to: ECG, blood pressure / pulse rate, blood sample for PK at defined time points, blood sample for safety.

Any meal will be served after the study-related measures / actions for a given time point have been completed.

9.2.4.1 Dosing and profile day (Study Day 1, relative time: day 00) - amended

The following measures / actions will be performed at the time points given in the study flow chart in Section 16.1.

- Fasting to be continued until the capillary glucose pre-dose is performed (drinking of water and beverages with artificial sweeteners is allowed)
- Abbreviated physical examination
- After a bed rest for at least 10 min, the following baseline measurements will be carried out: 12-lead ECG, vital signs (blood pressure/pulse rate, body temperature), blood sample (fasting capillary blood glucose, PK²⁶)
- Open questioning for / documentation of AEs and previous/concomitant medication (update)
- Low glyceic breakfast at 1.5 h prior to start of the infusion (for details, see Section 9.2.6.2)
- BP will be measured at least 2 times with 5-10 min intervals prior to the administration of the study drug until 2 consecutive values are <150/90 mmHg (see Sections 7.4 and 9.6.3 for further details)
- Study drug administration i.v. (approximately 8 a.m. for the first subject) (see Section 7.4.2)

²⁶ “Protein binding assessment” deleted before dosing according to Amendment 1

- Throughout the day until 12 h p.a.:
 - Capillary glucose 1h after start of copanlisib infusion (end of infusion), 1, 2, 3,²⁷ 6, 8 h after start of infusion, further capillary glucose if necessary
 - Further capillary glucose assessment at the discretion of the investigator (based of previous blood glucose levels)
 - Vital signs (blood pressure/pulse rate, body temperature) after a least 10 min in supine position at 1 h after start of copanlisib infusion (end of infusion) and at 6 h after start of infusion
 - 12-lead ECG after a least 10 min in supine position at 1 h after start of copanlisib infusion (end of infusion) and at 6 h after start of infusion
 - blood sampling for pharmacokinetics at 10 min after start of copanlisib infusion, at 1 h after start of copanlisib infusion (end of infusion) and at 1.5, 2, 2.5, 3, 5, and 8 h after start of infusion

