9.5 Pharmacokinetics / pharmacodynamics

9.5.1 Pharmacokinetics

9.5.1.1 Drug measurements

Blood samples for pharmacokinetic analyses of copanlisib and its metabolite BAY 84-5795 (M-1) in plasma will be collected at the time points given below and in the study flow chart, see Section 16.1. Urine for PK analyses of copanlisib and its metabolite M-1 will be collected in intervals given below and in the study flow chart (Section 16.1).

Blood samples for PK will be collected before start of infusion as well as at 10 min and 1 h (end of infusion [EoI]), 1.5, 2, 2.5, 3, 5, 8, 24, 48, 72, 96, 120 and 168 h after start of infusion (SoI).

Urine samples for PK will be collected in two sampling intervals from 0-8 and >8 up to 24 h after start of copanlisib infusion.

For all subjects, additional blood sample for evaluation of protein binding of copanlisib will be collected at 1 h after SoI (at EoI) on Day 1, and at 24 h after SoI on Day 2. These samples will be used for determination of fraction unbound and concentrations of total plasma protein, albumin and alpha 1-acid glycoprotein.

Whenever possible, all efforts should be made to adhere to the planned blood sampling schedule for PK. However, based on practical considerations, the following time ranges are provided as guidance:

- Pre-dose samples should be collected within 30 min before SoI.
- The end-of infusion sample for copanlisib and M-1 metabolite should be collected within 5 min after the end of infusion (EoI) of copanlisib for adequate characterization of C_{max} .
- For planned time points ≤ 6 h post-dose, PK samples should be collected within ± 15 min of the planned time.
- For planned time points > 6 h and ≤ 24 h, PK samples should be collected within ± 30 min.
- For planned time points > 24 h, the PK sample should be taken within ± 3 h.

It is of importance that the actual date and time of blood sampling are thoroughly documented in the electronic case report form (eCRF) because PK calculations will be based on the actual sampling times relative to dosing times. Deviations from the specified time points will be documented and taken into account when calculating the PK parameters.

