9.6.1.7 Recommendations for the management of specific adverse events

9.6.1.7.1 Management of glucose increases that can occur with study treatment

Management of transient post-infusion glucose increases in non-diabetic subjects

- Asymptomatic transient glucose increases
Mild to moderate asymptomatic increases of blood glucose may occur after study drug infusion, with larger increases potentially occurring post-prandial. Transient asymptomatic glucose increases that are ≤ 250 mg/dL do generally not require treatment with glucose-lowering medication. Subjects with post-dose blood glucose > 250 mg/dL should have repeated laboratory glucose measurements to verify if the values are persistent or decreasing. If the repeated glucose values are decreasing, glucose levels may be followed without glucose-lowering medication if the subject is asymptomatic and if hydration status is normal as clinically assessed.
- Symptomatic or persisting glucose increases
Hydration status: If the subject has symptomatic glucose increase of any grade, hydration status should be clinically assessed. If the clinical assessment is consistent with dehydration, fluids should be given as clinically appropriate (orally or IV).
Glucose-lowering medication: Subjects with post-dose blood glucose > 250 mg/dL should have repeated laboratory glucose measurements to verify if values are persistent or decreasing. If a blood glucose level of > 250 mg/dL persists upon confirmation by repeated laboratory analysis, and/or the subject is symptomatic, and/or the hydration status indicates the need for hydration, glucose-lowering medication should be administered: Rapid or short-acting (regular) insulin may be given for blood glucose levels that are persisting at > 250 mg/dL, or if the subject is symptomatic during the infusion day. "Sliding scale" short-acting or (regular) insulin coverage of blood glucose levels that are persisting at > 250 mg/dL is recommended, with oral or IV hydration as clinically appropriate. Only the use of short-acting (rapid-acting) insulin is recommended for treatment of glucose increases after the single dose copanlisib infusion in non-diabetic subjects.
Meal timing is added to the glucose management log used by the investigator and to be continued as long as hyperglycemia induced by the copanlisib infusion persists.

Management of transient post-infusion glucose increases in diabetic subjects

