- Position: Supine (small pillow under head allowed) for at least 10 min
- Measuring site: cuff to be placed on the right / left upper arm (if possible, the same arm will be used for all measurements in one subject)
- Method: oscillometric by automatic measurement device

Body temperature, BP, and pulse rate will be assessed according to the schedule summarized in the flow chart in Section 16.1. If clinically indicated, it is at the investigator's discretion to perform these measurements more frequently.

BP will be measured every 5 to 10 min before the copanlisib dose until 2 consecutive values are <150/90 mmHg. A single BP measurement will be performed at the end of the copanlisib IV infusion.

For details about the management of arterial hypertension, see also Section 9.6.1.7.2 (treatment of arterial hypertension).

- **Body temperature**

Body temperature will be measured by a member of the investigator's team using always the same method according to local practice. The measured values are to be recorded in the electronic CRF in degree Celsius (°C).

- **Electrocardiogram**

A complete standard 12-lead ECG will be recorded by a member of the investigator's team under the following conditions:

- Position: supine (small pillow under head allowed) for at least 15 min
- Device: computerized ECG device
- Automatic calculation of the following parameters: RR interval, heart rate, P-duration, PR (PQ) interval, QRS-duration, QT (uncorrected). For data analysis by the sponsor, the frequency-corrected QT interval will be calculated according to both the formula of Fridericia (QTcF) and Bazett (QTcB) by data management.
- Evaluation of ECG by a physician providing an ECG diagnosis and overall assessment (including clinical relevance)

- **Laboratory examinations**

Blood and urine samples will be collected by a member of the investigator's team, for time points and parameters see Section 16.1 and Section 16.2 in the appendix.

The MDRD equation will be used for the eligibility assessment in Group B (see Section 16.5). The creatinine clearance will be calculated from the creatinine concentration measured in serum according to the Cockcroft-Gault formula after the study (see Section 16.6).

In the event of implausible results, the laboratory may measure additional parameters to assess the quality of the sample (e.g. clotted or hemolyzed) and to verify the results.

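### No blood-pressure reading is required during the 1-hour infusion, so for a symptom-free rise the advice to treat, interrupt or slow depends on discretionary readings

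*Protocol*

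**What the plan says.** Protocol Section 9.6.1.7 is headed "Recommendations for the management of specific adverse events", so what follows is guidance. Within it, Section 9.6.1.7.2 suggests antihypertensive treatment if pressure reaches 150/90 mmHg during the infusion. If hypertension of 160/100 mmHg or more "occurs during copanlisib IV infusion, the copanlisib IV infusion should be interrupted or slowed down, administration of anti-hypertensive therapy initiated", the infusion may restart once pressure is back below 150/90 mmHg.

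Three places set the timing of readings, and they agree:

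- Section 9.6.3 requires readings every 5 to 10 minutes before the dose until two consecutive values are below 150/90 mmHg. Then: "A single BP measurement will be performed at the end of the copanlisib IV infusion".
- Section 9.2.4.1 lists "Vital signs (blood pressure/pulse rate, body temperature) after a least 10 min in supine position at 1 h after start of copanlisib infusion", which is the end of infusion, and again at 6 h.
- The vital-signs row of the flow chart (Section 16.1) has a mark 30 minutes before the start and at 1 h, and none at 0 or 10 minutes.

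Section 9.6.3 also has a permissive clause: "If clinically indicated, it is at the investigator's discretion to perform these measurements more frequently".

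When procedures coincide, Section 9.2.4 sets the order as "ECG, blood pressure / pulse rate, blood sample for PK at defined time points". Section 9.5.1.1 fixes the draw: "The end-of infusion sample for copanlisib and M-1 metabolite should be collected within 5 min after the end of infusion".

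**The concern.** Interrupting or slowing an infusion helps only while drug remains to be given. The protocol sets two thresholds that apply during the infusion but requires no measurement in that window. A symptomatic subject would presumably be measured under the permissive clause. A rise without symptoms gives no clinical indication for an extra reading, so under the minimum schedule it is first seen at the end.

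Section 3 names hypertension as an expected effect of the class. It also counts monitoring among the measures that protect subjects from undue risk. The only 12 mg experience it describes for safety is six healthy subjects in the mass balance study. The subjects with hepatic or renal impairment are a different population, and Section 7.4.2 lets them be dosed after antihypertensive medication given the same day. What is at stake is a modest, avoidable gap in safety monitoring. A secondary issue is that interruptions, when they occur, affect Cmax, one of the three primary variables.

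**Working it through.** The plan gives no figure of its own here, so there is none to reproduce.

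**Step 1. Count the readings.** Required readings strictly between 0 and 60 minutes: Section 9.2.4.1, 0; Section 9.6.3, 0; flow chart, 0. The one procedure timed inside the infusion is the PK draw at 10 minutes, with no pressure reading attached.

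**Step 2. Drug left to withhold.** Section 7.1 gives 12 mg over 1 h. A constant rate is my assumption: 12/60 = 0.2 mg/min.

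| Time of reading | Drug left | Share of dose |
|---|---|---|
| 30 min | 12 − 0.2 × 30 = 6.0 mg | 50% |
| 55 min | 12 − 0.2 × 55 = 1.0 mg | 8.3% |
| 60 min | 0 mg | 0% |

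Because pressure precedes the PK draw, and that draw is due within 5 minutes after the end, I place the end-of-infusion reading in the last 5 minutes or at the end. That leaves 0 to 1 mg.

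**Step 3. What an interruption does to Cmax.** PK is taken as linear (Section 7.4.1 describes it as dose-linear), and the infusion is halted at 30 minutes.

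- *Not resumed.* If the disposition curve does not increase with time, its integral over 0–30 min is at least half that over 0–60 min. Cmax is therefore at least 50% of the uninterrupted value. AUC falls by 50%, because half the dose is given.
- *15-minute pause, then full rate.* With mono-exponential disposition and x the fraction remaining after 15 min, the Cmax ratio is (1 + x³)/(1 + x²). The minimum is at x³ + 3x − 2 = 0, so x ≈ 0.596 (half-life about 20 min). The ratio there is 0.894, a fall of about 11%. At the 38.2 h half-life in Section 3 it is 0.998.
- *60-minute pause, then full rate.* With y the fraction remaining after 30 min, the ratio is (1 + y³)/(1 + y) = 1 − y + y². The minimum is 0.75 at y = 0.5 (half-life 30 min), a fall of 25%.

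For a sum of exponentials with positive weights, the ratio is a weighted average of mono-exponential ratios, so the two pause bounds still hold. The documents give no pause length; 15 and 60 minutes are illustrations.

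**Step 4. Effect on the group geometric mean.** One affected subject with ratio r multiplies it by r^(1/n).

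| Case | r | n = 8 | n = 6 |
|---|---|---|---|
| 15-min pause | 0.894 | 0.986 (−1.4%) | 0.981 (−1.9%) |
| 60-min pause | 0.75 | 0.965 (−3.5%) | 0.953 (−4.7%) |
| Not resumed | 0.50 | 0.917 (−8.3%) | 0.891 (−10.9%) |

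**Step 5. Scale.** Section 10.4 gives a geometric CV for Cmax of 63.2% (Study 16270) and 73.3% (Study 12871). Log SD = √ln(1 + CV²) = 0.580 to 0.656. The 90% CI factor is exp(t × SD × √(2/n)):

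- 8 v 8 (14 df, t = 1.761): 1.67 to 1.78.
- 6 v 6 (10 df, t = 1.812): 1.83 to 1.99.

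A single affected subject is small against that imprecision.

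**The case against.** The strongest reply is that the risk does not warrant a change. The dose is 12 mg, 12/60 = 20% of the recommended 60 mg, and Section 3 calls the probability of these events very low at that dose. The six healthy subjects given 12 mg had no clinically relevant vital-sign changes. Uncontrolled hypertension is excluded (Section 6.2.1), and two consecutive pre-dose values below 150/90 mmHg are required (Section 7.4.2). Subjects are in-house, the investigator's team gives the infusion, and antihypertensives are to be at hand. The hypertension rates in Section 3 (21.1% and 60.5%) come from cancer patients and carry no timing, so nothing shows that pressure would rise within the hour. All of this stands, and it keeps the point small. It does not supply a required reading.

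A second reply is that mandated readings might cause more interruptions, perhaps more often in impaired subjects than in controls, and so bias the Cmax ratio downwards. That is fair. Such interruptions would follow from the sponsor's own thresholds, however, and those already apply to any rise that is noticed.

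Three stronger readings are tempting, and the documents do not support them:

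- *That the interrupt-or-slow step cannot work.* It can, whenever staff choose to measure during the infusion, which Section 9.6.3 allows. The end-of-infusion reading can also still prompt drug treatment.
- *That one mid-infusion reading closes the gap.* It leaves two stretches of about 30 minutes. The resumption rule also names a pressure without a repeat interval.
- *That the permitted agents belong to this point.* The guidance says "Topical nitrates, verapamil and diltiazem (nondihydropyridine calcium channel blockers) can be also considered", and Table 16-5 lists verapamil and diltiazem as moderate CYP3A4 inhibitors. That is a separate question, and Section 8.1 already has all concomitant medication documented.

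**Conclusion.** The point holds in a limited form. No reading is required during the infusion, so for a rise without symptoms the advice at both thresholds depends on discretion. The first required reading comes when 0 to 8% of the dose remains, assuming a constant rate and a reading in the last 5 minutes or at the end. Practical risk is low. The documents give no distribution or time course of blood pressure, so the number of subjects who would reach 160/100 mmHg cannot be estimated. Nor can it be shown that a 30-minute reading would catch them; 30 minutes is simply the midpoint. This is a cheap improvement to safety monitoring and does not threaten the study's conclusions.

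**What to change.** - Add at least one mandatory reading at about 30 minutes after the start of infusion (supine, with the oscillometric device already specified) to Sections 9.2.4.1 and 9.6.3 and to the flow chart. Leave the thresholds and actions unchanged.
- If the infusion is interrupted or slowed, repeat the reading every 5 to 10 minutes, the interval already used pre-dose, until it is below 150/90 mmHg.
- Record actual stop, restart and rate-change times. Section 9.6.1.2.4 already has an action category for interruption, and Section 11.3 already transfers actual dosing times, but neither names these.
- Take the end-of-infusion PK sample at the actual end of infusion, and flag affected subjects when Cmax is interpreted.

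The cost is one flow-chart entry, a few sentences and one extra cuff reading per subject, with no new staff, device or invasive procedure. The real downside is a possible small increase in interruptions, with the Cmax effects shown in the working. Recording the times makes those effects visible but does not undo them.
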